## 1. Title

Assessing body composition in trans gender males in hormonal therapy using bioimpedance analysis compared to dual x-ray absorptiometry.

## 2. Background, aims and hypothesis

### 2.1. Background

#### 2.1.1. Standard care in trans gender persons

0,55% of the Danish population are gender incongruent and 0,10% defines themselves as trans gender.

These are equally distributed as trans men and trans women. Some of these need gender affirming hormone therapy and gender affirming surgery (GAS). In Denmark, the requirements for surgery are a BMI<27 and BMI<35 for hormone therapy (Frisch et al., 2019). Endogenous sex steroids such as testosterone and estradiol play important roles in the accumulation and distribution of body fat and lean body mass and thus in the feminization and masculinization of body composition (Wells, 2007).

#### 2.1.2. Methods for assessment of body composition

The golden standard for measuring body composition is using body imaging techniques as magnetic resonance imaging (MRI) and computed tomography (CT). They are considered very precise imaging systems. They can separate fat from other soft tissues in the body, making these methods the gold standard for estimating muscle mass in research. Alternatively, dual x-ray absorptiometry (DXA) is an attractive method for research and in the clinic to distinguish fat, lean tissue, and bone mineral. This whole-body scan exposes the patient to minimal radiation compared to CT. The main limitation with this method is that the equipment is not portable, which may hinder its use in large scale (Cruz-Jentoft et al., 2010).

Bioimpedance analysis (BIA) estimates the volume of fat and lean body mass. The test itself is easy to use, readily reproducible, suitable for outpatient clinic patients and inexpensive. BIA measurements under standard conditions have been found to correlate well with MRI. Predictions have been validated for multiethnic adults and reference values established for adult white men and women, including older subjects (Cruz-Jentoft et al., 2010). BIA equipment does not measure muscle mass directly, but instead derives an estimate of muscle mass based on whole-body electrical conductivity. BIA uses a conversion equation that is calibrated with a sex specific reference of DXA-measured lean mass in a specific population (Cruz-Jentoft et al., 2019). Therefore, BIA prediction models are most relevant to the population in which they have been derived – mainly healthy subjects and in patients with stable water and electrolyte balance with a validated BIA equation that is appropriate with regards to age, sex and race. The conversion

equations used may therefore algorithmically exclude certain minorities as trans gender persons (Albert & Delano, 2021; Kyle et al., 2004).

Palle et al. (2016) investigated the relationship between single cross-sectional MRI of the thighs, skeletal muscle mass as reference and multi-frequency BIA fat free mass (FFM) (using Tanita MC-780 MA) in 18 patients (10 males and 8 females) with colorectal cancer undergoing chemotherapy. They found that BIA overestimated FFM for all measurements with a mean of 12,4 kg (SD 6,2). BIA showed a constant (and therefore correctable) error compared to MRI single cross-sectional of the thighs. Part of this difference may be related to the software/equations for calculation of body composition used in the BIA (Palle et al., 2016).

### 2.1.3. Body composition in trans gender persons in hormonal therapy

Persons with gender incongruence are treated with exogenous steroids to obtain the physical phenotype of the identified gender, including a feminine or masculine body fat distribution, musculature, and body shape. Klaver et al. (2017) showed that, during the first year of cross-sex hormone therapy, total body fat increases and total lean body mass decreases in transwomen, while the opposite occurs in transmen (Klaver et al., 2017). In 2018, Klaver et al. found that cross-sex hormone therapy also causes a more feminine body fat distribution and a lower waist-to-hip ratio in transwomen and a more masculine body fat distribution with a lower hip circumference in transmen (Klaver et al., 2018). For both studies they used DXA-scans to assess body composition (Klaver et al., 2017, 2018).

Van Velzen et al. (2020) measured 323 transmen and 288 transwomen using BIA at consecutive visits to the outpatient clinic from the start of hormone therapy to a maximum of 24 months follow-up. This prospective cohort study is part of the European Network for the Investigation of Gender Incongruence (ENIGI). They used the Tanita MC-780 MA for the BIA-measurement. They defined absence of change as transmen with a decrease in lean body mass or transwomen with a decrease in fat percentage. They found a lack of change in body composition in 20,2% of transmen and 9,4% in transwomen. In conclusion, they found a large variation in body composition changes during hormone therapy (van Velzen et al., 2020). ENIGI also published another study investigating the effect of estrone in feminizing hormone treatment. They measured 212 transwomen using Tanita MC-780 MA at baseline, after 3 months, and after 12 months of hormone treatment (Tebbens et al., 2022). In these two studies ENIGI measures trans persons using BIA without considering that the conversion equation is calibrated with a binary reference population. As mentioned above, as the hormone treatment progresses the body composition of a trans gender person change towards the identified gender. Therefore, using BIA to estimate body composition may not give a feasible estimation of fat mass and lean body mass.

#### 2.1.4. Using BIA in trans gender persons

Albert & Delano (2021) discuss the fact that BIA measurements are a product of proprietary regression equations that require a binary sex/gender as their input. Developing these regression equations Tanita, and other companies making BIA-measuring techniques, may not include a diverse background population which creates algorithmic exclusion. In practice, algorithmic exclusion means that the performance of these algorithms for individuals not in the original dataset are unknown, and that these algorithms likely work less well for those not included in the original dataset (Albert & Delano, 2021).

Generally, researchers suggest caution when using BIA working with populations that have altered body composition, such as patients with fluid overload, body shape abnormalities, altered fat/lean mass ratio etc (Kyle et al., 2004). In some of these cases, there are specific equations for a particular patient population, or alternative methods of body composition assessment that don't rely on regression (Keane et al., 2017).

#### 2.1.5. Gender affirming surgery in trans gender males

Although the World Professional Association for Transgender Health (WPATH) guidelines for GAS doesn't specify a BMI requirement (Coleman et al., 2012), as mentioned, in Denmark a BMI<27 is required. Such criteria serve as barriers to essential surgeries and do not have an empirical basis (Brownstone et al., 2021; Martinson et al., 2020). BMI has been widely criticized as a marker of health or wellness due to its two-dimensional nature. Trans gender persons tend to exhibit higher BMI for a range of reasons, including engagement in gender-affirming hormone treatment, higher risk of binge eating and related disorders (Diemer et al., 2015). It is commonly recognized that for those who wish to pursue medical transition, GAS improves health and quality of life (Nobili et al., 2018).

Body fat percentage, measured by BIA, can accurately reflect body adiposity, and serves as a better indicator for obesity (Kyle et al., 2004). Obesity, measured by body fat percentage, is significantly associated with increased surgical complication rate and may be a better indicator for obesity and predictor for postoperative complications than traditionally used BMI (Chun et al., 2013).

Therefore, as fat percentage in trans gender males are relevant to their treatment and alternatively gender affirmation surgery, including mastectomy, the precision of the estimation of body fat percentage using BIA may have real world impact. As seen in the studies above, researchers rely more and more on these estimates in their research and in the clinic.

## 2.2. Objectives

Hypotheses:

- By optimizing the use of sex specific reference values, we can improve the precision of the estimation of body fat volume using BIA measurements in trans gender males.

Aim:

- To assess body composition of trans gender males in hormonal therapy using BIA compared to DXA.
- To investigate whether binary reference values using BIA measurements in trans gender males in hormonal therapy is reliable – and thereby if BIA maybe a useful tool for assessing whether a trans gender man is suitable for mastectomy.

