### 3.2. Study population

Inclusion criteria:

- Trans gender males in hormonal therapy
- Age  $\geq$  18 years
- Ability to provide informed consent

Exclusion criteria:

- Inability to comprehend written consent form or provide informed consent
- BMI  $>$  35
- Pregnancy

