### 3.4.2. Bioelectrical impedance analysis (BIA)

In each patient body composition is measured using the “male” and “female” setting of the Tanita MC-780 MA, respectively. BIA-measurements take less than 1 minute, are without any side effects, and a part of standard care in this patient group when assigned for weight loss therapy at the Department of Health Promotion.

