## 4. Data collection

Following the participants’ informed consent, data regarding age, sex, medication, onset of hormonal therapy, and blood samples (p-alanine transaminase, p-albumin, p-alkaline phosphatase, p-bilirubin, B-erythrocytes, B-hemoglobin, p-estradiol, p-follicle stimulating hormone, Hb(B)-hemoglobin A1c, p-cholesterol (LDL), B-leucocytes, B-erythrocyte volume (MCV), p-prolactin, p-sex hormone binding globulin, p-testosterone, p-free testosterone, p-thyroid screening, B-thrombocytes, p-lutropin will be collected from the participants’ EPJ. The information gathered is for use in the research project only.

The participants will be measured on the BIA scale twice and once with DXA and they will be asked questions about their habits concerning smoking and exercise. The center for Gender Identity regularly refers trans gender persons to the Department of Health Promotion for weight loss therapy. Patients at the Department of Health Promotion are routinely weighed on the Tanita MC-780 MA-scale. The blood samples collected in this study are routine samples and collected as a part of the participants treatment plan. DXA scans are not standard procedure in this patient group and is the only part of this project which is not part of the patient’s regular treatment plan.

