#### 5.1.2. Statistical methods

Student's unpaired t tests will be used to compare variables between groups. Correlation analyses will be performed using Pearson's correlation coefficient. Wilcoxon rank-sum test will be used to compare nonparametric data between groups. Fischer's exact test will be used to test differences in cross tables.

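### Section 5.1.2 fixes unpaired tests and Pearson's r for BIA and DXA readings taken in the same person; paired bias and limits of agreement are needed, and aim 2 should stop at agreement with DXA

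*Protocol*

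**What the plan says.** - **Hypothesis and aims (protocol 2.2).** The hypothesis is that "By optimizing the use of sex specific reference values, we can improve the precision of the estimation of body fat volume using BIA measurements". Aim 1 is to assess body composition by BIA compared with DXA. Aim 2 asks whether binary reference values are reliable in this population, and "thereby if BIA maybe a useful tool for assessing whether a trans gender man is suitable for mastectomy".
- **Population (3.2, 5.1.1).** There is one population, "Trans gender males in hormonal therapy", with 10 participants and no comparison group.
- **Measurements (3.4.2, 4).** Every patient is measured with the male and the female "setting of the Tanita MC-780 MA, respectively". Section 4 confirms: "The participants will be measured on the BIA scale twice and once with DXA".
- **Tests (5.1.2).** "unpaired t tests will be used to compare variables between groups"; "Wilcoxon rank-sum test will be used to compare nonparametric data between groups"; "Correlation analyses will be performed using Pearson's correlation coefficient"; and Fisher's exact test for cross tables. The groups are not defined, and no paired method is named.
- **Limits the protocol sets itself (7).** The cohort is too small to improve the reference values. The data serve to compare BIA with DXA for body composition and to generate hypotheses.
- **Fat variable.** Section 2.2 speaks of fat volume, while the clinical rationale in 2.1.5 speaks of fat percentage.

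**The concern.** A method-comparison study has two questions to answer. How far is BIA from DXA on average (bias), and how much does that difference vary from person to person (scatter)? Both are properties of within-person differences.

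An unpaired t test on the same readings gives the right mean difference when all pairs are complete. Its standard error, however, is built from the spread between people, and it reports no within-person scatter. The rank-sum test also assumes independent groups. Pearson's r is unchanged when a constant is added to every BIA reading, so it cannot show bias.

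At stake is the answer to the main aim. A modest bias may come out non-significant while r gives no warning of it, and BIA could then be called reliable. Aim 2 would carry that result towards a surgical use for which the study collects no data.

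**Working it through.** **The plan's own figure.** Section 5.1.1 bases the 10 participants on clinical experience and gives no effect size, SD or power, so there is no calculation to reproduce. For orientation, a paired test at n = 10 and two-sided alpha 0.05 has 80% power for a mean difference of 1.00 SD of the differences.

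**Inputs.** n = 10 (5.1.1). Alpha is 0.05 (5.1.3), taken as two-sided. The protocol gives no SD for fat percentage, so two are assumed: between-person SD S = 7 points (range 5 to 9), equal for both methods, and SD of the BIA-minus-DXA differences D = 3 points (range 2 to 5). The implied within-person correlation is 1 − D²/(2S²) = 1 − 9/98 = 0.91.

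**Half-width of the 95% CI for the mean difference.**
- Paired: t(0.975, 9) × D/√10 = 2.262/3.162 × D = 0.715 D. With D = 3 this is 2.1 points (D = 2: 1.4; D = 5: 3.6).
- Unpaired: t(0.975, 18) × S × √(2/10) = 2.101 × 0.447 × S = 0.940 S. With S = 7 this is 6.6 points (S = 5: 4.7; S = 9: 8.5).
- Ratio: 6.58/2.15 = 3.1. Over the ranges it runs from 4.70/3.58 = 1.3 to 8.46/1.43 = 5.9.

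**Chance of a significant result** (simulation, bivariate normal, 100,000 studies per case; the paired values agree with the noncentral t).

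| True bias | S / D | Unpaired | Paired |
|---|---|---|---|
| 3 | 7 / 3 | 2% | 80% |
| 3 | 9 / 2 | 0.2% | 99% |
| 3 | 5 / 5 | 18% | 40% |
| 5 | 7 / 3 | 21% | above 99% |
| 6 | 7 / 3 | 42% | above 99% |
| 7 | 7 / 3 | 64% | above 99% |
| 8 | 7 / 3 | 82% | above 99% |

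The unpaired test becomes more likely than not to detect the bias near its own half-width of 6.6 points, which is where the table crosses 50%.

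**Pearson's r.** With S = 7 and D = 3, the median sample r is 0.92 at a bias of 0, 3 or 5 points. With S = 5 and D = 5 it is 0.52. What holds throughout is that r does not respond to bias, not that r is high.

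**What the paired analysis can deliver at n = 10.**
- The SD of differences is known to within √(9/χ²(0.975, 9)) = 0.69 to √(9/χ²(0.025, 9)) = 1.83 times its estimate.
- The upper limit of agreement lies 1.96 SD above the bias. Its exact 95% CI runs from 1.16 to 3.80 SD above the bias (noncentral t, 9 df, noncentrality 1.96√10, divided by √10).
- With an SD of 3, that limit is 5.9 points above the bias, CI 3.5 to 11.4. With SD 2 the CI is 2.3 to 7.6, and with SD 5 it is 5.8 to 19.0.

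**Aim 2 against the data collected.** Section 4 lists age, sex, medication, start of hormones, routine bloods, smoking and exercise habits, two BIA readings and one DXA. It lists no surgical decision, outcome or complication. The protocol gives no fat-percentage cut-off and no acceptable BIA–DXA difference; the only surgical criterion it cites is a BMI limit (2.1.1, 2.1.5).

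**The case against.** **Section 5.1.2 never mentions BIA against DXA.** It speaks of groups, and smoking, exercise and Fisher's exact test suggest that subgroup comparisons may be meant. Applying the unpaired test to BIA and DXA is therefore an inference. That stands, but it does not rescue the plan. No groups are defined, and on the subgroup reading Pearson's r is the only named method left for the main aim, and it cannot show bias. An unseen SAP could add detail, but the protocol itself has fixed the unpaired choice.

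**A reader might infer that bias would usually be missed and that r would look reassuringly high.** The documents do not support this. With the same assumed SDs, the unpaired test finds a 7-point bias in about 64% of studies and an 8-point bias in 82%, and r can be moderate within the assumed ranges. The only BIA error the protocol quotes is large: mean 12.4 kg, SD 6.2, for fat-free mass against thigh MRI in cancer patients (2.1.2). It is a different measure, reference and population, so it does not settle the size here, but it shows that 3 points is a choice and not a neutral value.

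**A reader might also infer that aim 2 reaches a conclusion on mastectomy suitability.** It does not. The wording is hedged, section 3.1 calls the study a pilot, section 8.3 says only that findings may contribute, and section 7 already narrows the purpose. Measurement validity is also a legitimate first step towards clinical use. What remains is that the aim reaches further than the data and section 7.

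**The hypothesis might seem to contradict section 7.** It need not: choosing better between the existing settings differs from improving the reference values.

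**Conclusion.** The analysis in 5.1.2 is wrong as written for the study's main comparisons. Those comparisons are within person, and the named methods are either for independent groups or insensitive to bias. This follows from the design and needs no assumed SD.

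The size of the consequence does depend on assumptions. With a between-person SD of 7 and an SD of differences of 3 fat-percentage points, a 3-point bias is significant in about 2% of studies unpaired against 80% paired. Over SDs of 5 to 9 and 2 to 5 the figures are 0.2–18% against 40–99%. The interval for the bias is about three times wider than it need be (1.3 to 5.9 times over the ranges). The supported statement is that a bias small relative to the between-person SD may be missed.

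The reach of aim 2 towards mastectomy suitability is a secondary matter of wording.

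**What to change.** 1. **Section 5.1.2.** For male setting against DXA, female setting against DXA, and male against female setting, report the mean paired difference with 95% CI, and the SD of differences with limits of agreement and their CIs. If a test is wanted, use a paired t or signed-rank test. Keep Pearson's r as description only, and unpaired tests only for true subgroups, which should be named.
2. **Section 2.2, variable.** State one fat variable and use it throughout.
3. **Section 2.2, aim 2 (secondary).** Limit the aim to agreement with DXA, and present surgical use as motivation or hypothesis generation, in line with section 7.

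**Cost.** Rewording and slightly more analysis on measurements already planned, with no new data. The claim becomes narrower, and at n = 10 the limits of agreement will be visibly wide. The pilot should report that imprecision openly.

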## 3. Methods

### 3.1. Study design

This pilot study will be performed as a cross-sectional study. There are currently no plans of a larger scale follow-up study. In case of a follow-up study a second application will be sent.

### 3.2. Study population

Inclusion criteria:

- Trans gender males in hormonal therapy
- Age  $\geq$  18 years
- Ability to provide informed consent

Exclusion criteria:

- Inability to comprehend written consent form or provide informed consent
- BMI  $>$  35
- Pregnancy

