## 5. Data analysis

### 5.1. Statistical methods

#### 5.1.1. Sample size

In this study we aim to include 10 participants. It was not possible to conduct a sample size calculation based on the reference data on the Tanita MC-780 MA-scale, as Tanita will not share their data or information about their population. We have a vast experience with DXA scans in the clinic, and from this

experience we know that 10 persons will be enough to detect a difference in body composition in a pilot study.

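### Does admitting participants at any stage of hormone therapy, with no analysis named for time on therapy, undermine the BIA-DXA comparison?

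*Protocol*

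**What the plan says.** Section 3.2 of the protocol includes "Trans gender males in hormonal therapy", aged 18 or over and able to consent, and excludes pregnancy and BMI above 35. It sets no minimum, maximum or stratum for time on therapy.

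Section 2.1.3 states that "as the hormone treatment progresses the body composition of a trans gender person change towards the identified gender" and then concludes: "Therefore, using BIA to estimate body composition may not give a feasible estimation of fat mass and lean body mass". It also reports from a cited cohort, followed for up to 24 months, that "they found a large variation in body composition changes during hormone therapy".

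Section 4 lists "data regarding age, sex, medication, onset of hormonal therapy" among the items taken from the patient record. Section 5.1.1 says "In this study we aim to include 10 participants". Section 5.1.2 names four generic methods, including "Correlation analyses will be performed using Pearson", and attaches no variable to any of them. The design is a cross-sectional pilot (section 3.1). Section 7 says the cohort is too small to improve the reference values and that the data are to serve further hypothesis generation.

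**The concern.** Read together, sections 2.1.3 and 3.2 seem to pull apart. If body composition shifts over time on treatment, the female setting might fit someone who has just started and the male setting someone years into therapy. Averaging the two could make both settings look moderately wrong although each suits part of the sample, and the average would move with the mix of early and late participants. The variable needed to see this, the onset date, is collected but not tied to an analysis. The second aim in section 2.2 links the result to judging suitability for mastectomy, so an answer driven by the enrolment mix would matter.

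**Working it through.** **1. Eligibility against the aim.** Section 2.2 asks about body composition, and about the reliability of binary reference values, in trans men on hormone therapy. Section 3.2 recruits that population, in the same terms and without a duration limit in either place. The two sections agree.

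**2. What the protocol commits to estimating.** No section defines a pooled mean BIA-minus-DXA error, and none says the study will choose between the male and female setting. Section 3.4.2 measures everyone on both settings, and the aim is to see whether such settings are reliable in this population. If a mixed-stage clinic population makes both settings miss, that answers the question asked.

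**3. What section 2.1.3 claims.** It says composition changes and that BIA may therefore be unsuitable. That the error varies with duration is a reasonable inference, but it is not stated. Sections 2.1.2 and 2.1.4 give a further reason for doubt, that equations may have been derived without trans people, and this does not depend on duration.

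**4. The size under an assumed model.** None of these inputs is in the protocol: a gap G of 5 to 10 fat-percentage points between settings, the female setting exact at month 0, the male setting exact at month 24, and a linear shift between.

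- Male-setting bias at t months = −G(1 − t/24); female-setting bias = G·t/24.
- All at 3 months: male −0.875G = −4.4 to −8.8; female +0.125G = +0.6 to +1.3.
- All at 24 months: male 0; female +5 to +10.
- Five at 3 months and five at 24: male −0.4375G = −2.2 to −4.4; female +0.5625G = +2.8 to +5.6.
- Female minus male bias = G·t/24 + G(1 − t/24) = G at every t, so the within-person contrast between settings does not depend on the mix.
- Male bias is never above 0 and female bias never below 0, so neither setting can look unbiased through cancellation.
- With G = 7, residual SD 3 and durations uniform over 0 to 24 months, the limits of agreement are ±1.96·√(9 + 49/12) = ±7.1, against ±1.96·3 = ±5.9. The wider limits correctly describe agreement in a mixed-stage population.

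**5. Mix against sampling error.** Let D be an assumed early-to-late difference in bias. Going from 2 to 8 late-stage participants out of 10 moves the mean by 0.6D: 1.2, 2.4 or 3.6 kg for D = 2, 4 or 6 kg. The only error SD in the protocol is 6.2 kg (section 2.1.2: fat-free mass, BIA against MRI, cancer patients, so illustrative only). It gives a 95% half-width of 2.262 × 6.2/√10 = 4.4 kg. Each of these shifts is smaller than that.

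**6. What an analysis by duration could deliver at n = 10.**

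- Critical |r| at two-sided 0.05 (sidedness assumed): 2.306/√(8 + 2.306²) = 0.632.
- |r| needed for 80% power (Fisher z): tanh((1.960 + 0.842)/√7) = 0.79.
- 95% CI for an observed r of 0.5: tanh(0.549 ± 1.96/√7) = −0.19 to 0.86.
- The model in step 4 implies a true correlation of √(49/12)/√(9 + 49/12) = 2.02/3.62 = 0.56. Its power is about Φ(0.631·√7 − 1.96) = Φ(−0.29) = 39%.

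Even if the assumed mechanism were exactly right, the study would more often miss it than find it.

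**The case for a change.** The strongest counter-argument is that the protocol's own reasoning makes time on therapy the obvious explanatory variable, that the date is already extracted, and that a pre-stated plot of the BIA-DXA difference against months since onset costs almost nothing and avoids a post-hoc choice. It would also suit the hypothesis-generating purpose in section 7, which names only small size as a limitation.

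The facts behind this stand: there is no duration criterion, the onset date is collected, and section 5.1.2 does not name it. But that section names no variable for any method, so the onset date is not singled out. The Pearson analysis could include it, and an SAP, which is not at hand, is the usual place to say so. The argument therefore supports a useful addition and does not show that the protocol states or fixes something wrongly.

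The further step, wording the conclusion on the settings by therapy duration, goes beyond what 10 participants can support. Duration may also be a weak proxy for where a person's body composition lies: the cohort cited in section 2.1.3 found no change, as it defined it, in 20.2% of transmen.

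**Conclusion.** The concern does not hold. The eligibility rule matches the aim, no stated analysis or decision rule is distorted by the mix of therapy stages, and heterogeneity by stage belongs to the population the study set out to describe. The illustrated sizes (male-setting bias anywhere from 0 to −8.8 points depending on the mix, limits of agreement of ±7.1 instead of ±5.9) follow correctly from their inputs, but the gap, the linear shift, the end points and the residual SD are all assumed. Reporting the range of therapy durations and displaying the differences against time since onset would help readers. That is a preference about presentation. This conclusion assumes that the results are reported as a pilot in trans men on hormone therapy generally, within the limits section 7 sets. A later claim that one setting fits at a particular stage would need a different study.
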